9.2.3 Suspected unexpected serious adverse reactions (SUSARs)

Not applicable

9.3 Annual safety report

Not applicable

9.4 Follow-up of adverse events

All AEs will be followed until they have abated, or until a stable situation has been reached. Depending on the event, follow up may require additional tests or medical procedures as indicated, and/or referral to the general physician or a medical specialist. SAEs need to be reported till end of study within the Netherlands, as defined in the protocol.

9.5 Safety Committee

Not applicable

10. STATISTICAL ANALYSIS

10.1 Primary study parameter

Network activity and functionality are measured and quantified by standard equipment and software, and presented in a descriptive way. Networks are considered functional when at least 1/3 of all electrodes shows activity, with a minimum of 6 spikes per minute per active electrode, and a minimum of one synchronous event per minute at eight weeks after plating.

Fifteen networks belonging to three independent batches will be cultured from each patient and control. The fraction of cultures that develops functional networks will be calculated.

10.2 Secondary study parameters

Electrophysiological responses to ischemia will be measured with our standard experimental set up.

Differences with regard to electrophysiological responses to ischemia will be analysed between patients and controls with parametric or non-parametric statistical tests, depending on normality of the data.

Variance of electrophysiological responses to ischemia will be analysed by means of two-way ANOVA and post hoc Bonferroni correction.

- Between patients, i.e. inter-patient variance
- Between networks from one individual subject, i.e. intra-patient variance

If responses to ischemia differ between patients, inter-patient variance should be larger than intra-patient variance.

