4. STUDY POPULATION

4.1 Population (base)

Ten patients with ischemic stroke will be included in this study. These patients should have clearly documented cerebral infarcts, confirmed by MRI or CT imaging. Patients will be included during follow up, at approximately six to eight weeks from stroke onset, or later.

hiPSCs from five age-matched control subjects from our repository will be used as controls.

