4.4 Sample size calculation

Sample size calculation is hampered by lack of data. A sample size of ten patients and five controls is based on feasibility considerations: cell lines, culturing, and measurements of 15 subjects are possible within 2 years and provide a first estimation of the feasibility of the objectives.

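### The patient-control comparison of ischemic responses names no unit of analysis, so clustered networks may be tested as if independent; the subject should be the unit

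*Protocol*

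**What the plan says.** Estimating the difference between patients and controls is part of the secondary objectives (Protocol section 2). For the analysis, section 10.2 states that differences in electrophysiological response to ischemia "will be analysed between patients and controls with parametric or non-parametric statistical tests, depending on normality of the data". No test is named, and nothing says whether one observation is a network or a person.

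The data come in clusters. Section 10.1 states: "Fifteen networks belonging to three independent batches will be cultured from each patient and control". Section 4.4 gives the number of people: "A sample size of ten patients and five controls is based on feasibility considerations". Section 4.1 gives the source of the comparison group: "hiPSCs from five age-matched control subjects from our repository will be used as controls". Section 8.1 says that the study parameters are obtained from networks in vitro, and section 8.1.2 defines the ischemic responses as network measurements. No section mentions averaging or otherwise summarising networks within a subject.

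Section 10.2 then turns to variability: "Variance of electrophysiological responses to ischemia will be analysed by means of two-way ANOVA and post hoc Bonferroni correction". It separates variance between patients from variance between networks of one subject, and adds: "If responses to ischemia differ between patients, inter-patient variance should be larger than intra-patient variance". This analysis is not linked to the patient-control comparison.

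**The concern.** Fifteen networks grown from one person's cells share that person's genome, reprogramming and cell line, so they are likely to resemble each other. The independent units for comparing patients with controls are the 10 and 5 people. The group-comparison sentence fixes the kind of test and the rule for choosing it, but not the unit. Since every response is a network value, an analyst following the text would have up to 150 patient values and 75 control values, and would apply a two-sample test to them.

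If networks from one subject are correlated, that test understates the standard error. Its p-value is too small and its confidence interval too narrow. A significant result could then reflect which 10 patients and 5 control lines were sampled. Switching to a rank test does not help, because it assumes the same independence.

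**Working it through.** The protocol gives no alpha, power, effect size or calculated sample size for this comparison (section 4.4: "Sample size calculation is hampered by lack of data"). There is no stated figure to reproduce, so the check asks what a network-level test would do.

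**Inputs from the protocol**
- Subjects: 10 patients and 5 controls (section 4.4).
- Networks cultured per subject: 15, in 3 batches (section 10.1).
- Networks in total: 10 × 15 = 150 patient and 5 × 15 = 75 control, 225 in all.

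**Assumptions**
- Two-sided alpha of 0.05.
- The ICC (share of total variance lying between subjects) is not given. A range of 0 to 0.5 is shown.
- The number of networks per subject that are functional, exposed to ischemia and analysable (m) is not given. Values of 15, 5 and 3 are shown.

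**Formula.** With m networks per subject, the design effect is DE = 1 + (m − 1) × ICC. If the test ignores clustering, the approximate false-positive rate is 2 × [1 − Φ(1.96 / √DE)].

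**Example.** For m = 15 and ICC = 0.1, DE = 1 + 14 × 0.1 = 2.4. Then 1.96 / √2.4 = 1.265, and the rate is about 0.206. The effective number of networks is 225 / 2.4 = 93.7.

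**Results for m = 15.** The simulation used 20,000 runs with 10 versus 5 subjects, a normal subject effect and no group difference.

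| ICC | DE | Formula | Simulated t-test on networks | t-test on subject means |
|---|---|---|---|---|
| 0 | 1.0 | 0.050 | 0.048 | 0.052 |
| 0.05 | 1.7 | 0.133 | 0.134 | 0.047 |
| 0.1 | 2.4 | 0.206 | 0.202 | 0.048 |
| 0.2 | 3.8 | 0.315 | 0.320 | 0.049 |
| 0.3 | 5.2 | 0.390 | 0.401 | 0.053 |
| 0.5 | 8.0 | 0.488 | 0.506 | 0.050 |

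A Mann-Whitney test on networks (3,000 runs) agreed with the t-test within about 0.02. Repeat simulations moved individual entries by about one percentage point, hence the rounded ranges quoted elsewhere.

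**Fewer analysable networks (formula)**

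| m | ICC 0.1 | ICC 0.5 |
|---|---|---|
| 5 | 0.098 | 0.258 |
| 3 | 0.074 | 0.166 |

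**Where 0.5 comes from.** If section 10.2's criterion is read as a statement about variance components, inter-patient variance above intra-patient variance means ICC > 0.5. That is what would be seen if the study's hypothesis proved true. It is not a value that the protocol assumes.

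**Precision with the subject as unit.** A two-sided 5% t-test of 10 versus 5 subject means (13 degrees of freedom) has 80% power for a difference of about 1.66 SD of subject means. Treating 150 versus 75 networks as independent would suggest 0.40 network-level SD. These are different scales. With 15 networks per subject and no batch variance, 1.66 converts to 1.66 × √(0.1 + 0.9/15) = 0.66 network-level SD at ICC 0.1, and 1.66 × √(0.5 + 0.5/15) = 1.21 at ICC 0.5. On a common scale the gap is about 1.7-fold to 3-fold.

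**The case against.** The strongest reply is that the protocol never says networks are the unit, nor that they are independent. It speaks of comparing patients with controls, who are people. A test on one summary per subject fits the sentence, needs no subject term and keeps the 5% level. A mixed model also counts as parametric. The authors plainly know that networks are nested in subjects, because the next paragraph separates the two sources of variance. Details of the model are often left to a statistical analysis plan. All of this stands against a reader inferring that the protocol prescribes an invalid test, or that false differences will be common. The first is not stated, and the second depends on two quantities that are not given.

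A reader might also take section 10.2 to expect an ICC above 0.5. It does not: the sentence is conditional and sets out how a difference between patients would be recognised. Nor does section 10.1 say that all fifteen networks will enter the ischemia analysis. Fifteen is the number cultured, and with fewer the inflation is smaller.

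The point survives these replies. The protocol does not leave this analysis open: it fixes the class of test and the rule for choosing it, and omits the element on which validity depends. Every measurement it describes is a network value, and no per-subject summary appears anywhere. The two-way ANOVA addresses variability and is not tied to the group comparison.

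**Conclusion.** The concern holds as a defect of specification with a potentially large effect. Section 10.2 permits, and most naturally leads to, a test that counts clustered networks as independent. If networks are pooled, the nominal 5% error becomes about 13 to 14% at ICC 0.05, 20 to 21% at 0.1, 32% at 0.2 and 50% at 0.5 with 15 networks per subject. With 5 networks it becomes about 10% at ICC 0.1 and 26% at ICC 0.5. At an ICC of zero there is no inflation. These figures assume normal subject effects, equal variances in the two groups and equal numbers of networks per subject.

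The documents do not support the stronger conclusion that the plan treats networks as independent. The reach is also limited. The comparison is secondary, the sample size rests openly on feasibility, and the primary outcome is a descriptive fraction of functional cultures that this does not touch.

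**What to change.** State in section 10.2 that the subject is the unit of inference for the patient-control comparison and that networks are not treated as independent observations. Then choose one of two methods:

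- **One summary per subject.** Reduce each subject's networks to one value and compare 10 with 5, for example by a t-test or an exact permutation test.
- **A linear mixed model.** Use group as fixed effect, random intercepts for subject and for batch within subject, and small-sample degrees of freedom.

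These are alternatives and need not give the same answer, so one should be named in advance. In either case, report the difference with its 95% confidence interval, which suits the stated aim of estimating differences.

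The cost is one paragraph of text and no new data. Confidence intervals will be wider than a network-level analysis would show, because they then reflect the 15 people studied.

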2. OBJECTIVES

Primary Objective:

To generate functional neuronal networks from induced pluripotent stem cells (iPSCs) derived from patients with ischemic stroke

Secondary Objectives:

To measure neuronal network responses to simulated cerebral ischemia, estimate differences between patients and controls, and estimate variation amongst patients.

Tertiary Objectives

To relate ischemic responses to patient characteristics and to neuronal properties

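### The variance analysis names only patients and networks and omits the batch level of the design, so if batches are nested in subjects the patient test uses too small an error term

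*Protocol*

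**What the plan says.** The secondary objectives in Protocol section 2 include to "estimate differences between patients and controls, and estimate variation amongst patients". Section 10.2 gives the method for the second part: "Variance of electrophysiological responses to ischemia will be analysed by means of two-way ANOVA and post hoc Bonferroni correction". Two sources follow: "Between patients, i.e. inter-patient variance" and "Between networks from one individual subject, i.e. intra-patient variance". The section then says how the result is to be read: "If responses to ischemia differ between patients, inter-patient variance should be larger than intra-patient variance".

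The data structure is set out in section 10.1: "Fifteen networks belonging to three independent batches will be cultured from each patient and control". On patients, section 4.1 says: "Ten patients with ischemic stroke will be included in this study". The variance analysis therefore covers 10 × 15 = 150 patient networks if all are usable.

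Section 10.2 does not mention batch and does not name the two ANOVA factors. No section says whether a batch is a culture run shared by several subjects or belongs to one subject.

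**The concern.** Networks from one batch share plating, medium and handling, so their responses may be correlated. If each subject has its own three batches, a patient's mean rests on three independent units, not fifteen. An analysis that knows only patients and networks judges differences between patients against the scatter of single networks. That scatter understates how far patient means move apart through batch alone.

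The risk is that ordinary culture variation is partly reported as a difference between patients in their response to ischemia. Section 10.2 fixes the method, the two sources and the reading of the result, so this is not detail left to a later analysis plan. The stated sources do not match the design in section 10.1.

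**Working it through.** The protocol gives no power, significance level or variance for this analysis, so there is no figure of its own to reproduce.

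**Inputs from the protocol.** 10 patients (section 4.1); 15 networks in 3 batches per subject (section 10.1).

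**Assumptions.** Balanced data, so 15 / 3 = 5 networks per batch; one analysed value per network; normal errors; 5% level; total variance 1; no true patient variance; batch share ρ of total variance from 0 to 0.5.

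**Degrees of freedom.** Patients 10 − 1 = 9; batches within patients 10 × 2 = 20; networks within batches 10 × 3 × 4 = 120; all networks within patients, batch ignored, 20 + 120 = 140.

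**Expected mean squares, batches nested in patients** (σp², σb², σe² for patient, batch and network):

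- Patients: σe² + 5σb² + 15σp²
- Batches within patients: σe² + 5σb²
- All networks within patients, batch ignored: σe² + (20 × 5 / 140)σb² = σe² + 0.714σb²

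With σp² = 0, only the second line matches the first, so batch within patient is the correct error term.

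**Bias of the patient component when batch is ignored.** (5 − 0.714)σb² / 15 = 0.286σb², about 29% of batch variance. With total variance 1 the apparent patient share is 0.286ρ: 0.029, 0.057 and 0.086 at ρ = 0.1, 0.2 and 0.3.

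**False-positive rate for a patient difference** (20,000 simulated data sets per setting, 10 × 3 × 5, batches nested):

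| Batch share ρ | Batch ignored, F(9,140) | Patient × batch number, residual error, F(9,120) | Nested, F(9,20) |
|---|---|---|---|
| 0 | 4.8% | 4.9% | 4.8% |
| 0.05 | 11.9% | 13.7% | 5.0% |
| 0.10 | 21.8% | 26.7% | 5.1% |
| 0.20 | 42.9% | 55.8% | 5.0% |
| 0.30 | 60.9% | 77.4% | 4.9% |
| 0.50 | 82.6% | 96.5% | 5.1% |

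The third column can be checked exactly. The F ratio is inflated by k = (1 − ρ + 5ρ) / (1 − ρ), and the rejection rate is P[F(9,120) > Fcrit / k]. At ρ = 0.10, k = 1.4 / 0.9 = 1.556, which gives 26.6%. At ρ = 0.20, k = 1.8 / 0.8 = 2.25, which gives 55.4%.

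**If batches are shared by all patients, without interaction.** A patient × batch two-way ANOVA rejects in 4.8% to 5.0%, as it should. The nested test would then be far too conservative: 1.5%, 0.5% and 0.2% at ρ = 0.1, 0.3 and 0.5. The structure must therefore be stated before a test is fixed.

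**Power of the correct nested test.** At patient share 0.20 and batch share 0.10, the ratio of expected mean squares is (0.70 + 0.50 + 3.00) / (0.70 + 0.50) = 3.5. P[F(9,20) > 2.393 / 3.5] is about 72%. Ignoring batch gives 95%, but that test does not hold its level.

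**The stated reading of the result.** It is not a test under either meaning of variance. As mean squares, between exceeds within in about 44% of data sets with neither a patient nor a batch effect. As variance components, a real patient share of 0.20 still leaves 0.20 between against 0.80 within, so the condition fails although patients differ.

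**The case against.** Four objections deserve weight.

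1. **Nesting is inferred.** Section 10.1 does not say whether culture runs are shared across subjects. If they are, and there is no interaction, a patient × batch two-way ANOVA is valid. This stands and makes the point conditional. It does not rescue the text, because section 10.2 lists networks, not batch, as the second source.

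2. **The rejection rates belong to an F test at 5%, and section 10.2 states no level.** Its stated comparison, taken as variance components with batch ignored, is almost never met without a patient effect: 0.0% at batch shares 0.05 to 0.30. This stands as a limit on what the rates describe. They describe the patient test that an ANOVA delivers.

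3. **The bias is small.** A shift of 0.03 to 0.09 in the patient share is modest beside the uncertainty of a variance estimated from ten patients. True of the estimate, but not of the test, whose error rate more than doubles at a 5% batch share.

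4. **The aim is secondary.** Section 4.4 sizes the study on feasibility, and the primary outcome is a descriptive fraction. This stands and lowers the priority.

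A reader might also infer that the planned ANOVA cannot be fitted, because a patient × network table with one value per cell has no residual. The documents do not support that: the factors are not named, and nothing says that each network gives a single response. Section 8.1.2 lists several responses, and section 8.3 describes continuous recording.

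**Conclusion.** The point holds in conditional form. Section 10.2 omits a level that section 10.1 builds in. If batches are nested in subjects, which is the natural reading, testing patients against pooled networks raises a nominal 5% error rate to about 12%, 22%, 43% and 61% at assumed batch shares of 5%, 10%, 20% and 30%. The protocol gives no batch variance; at zero there is no inflation.

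Two stronger readings are tempting but not supported. One is that batch variation is simply read as patient variation: only about 29% of it moves to the patient component. The other is that the study's main conclusion is at risk: the primary objective is to generate functional networks, and its descriptive outcome is untouched. The point should be fixed; confidence is medium, because nesting is inferred.

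**What to change.** In section 10.2, replace the two-way ANOVA with a random-effects (mixed) model with patient, batch and network:

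- State whether batch is nested within patient or, where culture runs are shared, crossed with patient.
- Test the patient component against the error term that this structure implies: batch within patient if nested. The 9 and 20 degrees of freedom apply only if all batches are complete. Section 10.1 expects only a fraction of cultures to become functional, so they should not be fixed in the text.
- Report the variance components with 95% confidence intervals, and base the conclusion that patients differ on these instead of the bare larger-than comparison.
- Bonferroni pairwise comparisons (10 × 9 / 2 = 45 patient pairs) may stay as a supplement, but they do not estimate variance.

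The cost is analysis wording and a record of which batch each network came from. No further blood, lines or cultures are needed. Power is lower but honest: about 72% instead of an invalid 95% at patient share 0.20 and batch share 0.10, if batches are nested.

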8.3 Study procedures

Procedures in patients

All patients with acute brain infarcts will be admitted to a stroke unit to receive diagnosis and treatment as usual, as described in national and local stroke unit protocols. Standard CT or MRI, CT-angiography, CT-perfusion, and measures of neurological impairment and functional recovery are collected in the context of current care.

Patients will be informed about the study after admission on the stroke unit or at the time of follow up by the treating physician. If the patient gives permission, the treating physician will contact the research coordinator or study nurse. The research coordinator or study nurse will then contact the patient and provide additional information, both orally and written. The patient will be able to read the information carefully, discuss with family and ask questions. Patients will have at least one week to consider participation. . Inclusion will take place at the time of follow up, approximately six to eight weeks after infarction.

After oral and written informed consent, 30cc of venous blood in heparin anticoagulant (3x10cc) will be collected, handled, and stored according to local guidelines. Blood samples from patients will be collected during routine follow up at the hospitals outpatient department. Blood samples will be collected during routine blood sampling, if possible. If not, there will be one additional puncture. There will be no additional hospital visit.

Procedures in blood samples

Blood samples will be transported to University of Twente, CNPH lab, for further work-up and analysis. In short, we will generate iPSCs lines by exposing lymphoblast to reprogramming factors using a non-integrating episomal plasmid system to acutely express the Yamanaka reprogramming factors.^{15,16} hiPSC clones will be validated for pluripotency and genomic integrity through a standardized battery of quality control tests. iPS cells will be directly derived into excitatory and inhibitory neurons as published previously.¹⁷ Physiological ratios of excitatory and inhibitory neurons will be grown on Multiwell-MEAs for non-invasive, continuous recording of network functioning through extracellular electrodes. In parallel, cultures plated on coverslips will be fixed in 4% paraformaldehyde in 0.1M PBS at pH 7.4 for immunocytochemical staining (Figure 1). Staining protocols are available on request.

[figure not shown]

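### Section 10.2 compares patients with networks only; clones per subject and their link to batches are not fixed, so clone or batch variation can pass for inter-patient variation

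*Protocol*

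**What the plan says.** Section 8.3 describes reprogramming in summary form: "we will generate iPSCs lines by exposing lymphoblast to reprogramming factors", after which "hiPSC clones will be validated for pluripotency and genomic integrity through a standardized battery of quality control tests". No number of lines or clones per subject is given.

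Section 10.1 fixes the replication: "Fifteen networks belonging to three independent batches will be cultured from each patient and control". It does not say whether a new batch is a new clone or a new differentiation of the same clone.

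Section 10.2 names two levels of variance for the ischemic responses: "Between patients, i.e. inter-patient variance" and "Between networks from one individual subject, i.e. intra-patient variance". It adds that the first should exceed the second if patients differ. The method is a two-way ANOVA whose factors are not named. Neither clone nor batch is listed as a level.

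Controls are existing lines: "hiPSCs from five age-matched control subjects from our repository will be used as controls". On numbers of subjects, section 4.4 says "Sample size calculation is hampered by lack of data" and "A sample size of ten patients and five controls is based on feasibility considerations".

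**The concern.** A clone is a level of biological variation between the patient and the network. If a patient is represented by one clone, whatever is peculiar to that clone is shared by all fifteen networks and adds to the variance between patients. More networks or batches from the same clone do not remove it. The number of clones is settled when the cultures are grown, so a later analysis cannot recover the separation.

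If clones or batches do differ within a patient, the networks of one batch resemble each other. Fifteen networks then carry less information than fifteen independent observations, and a comparison against network variance is too liberal.

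At stake is the secondary objective of estimating variation amongst patients, and the rationale in section 1 that networks may show how vulnerable a particular patient is to ischemia.

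**Working it through.** **Inputs from the protocol.** 10 patients (4.4); 15 networks in 3 batches per subject (10.1). The protocol has no power or variance figure to reproduce.

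**Assumptions.** 5 networks per batch (15 / 3); a 5% test; true patient variance zero, so every positive finding is false; clone and batch variances over a range.

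**Notation.** Variances: N network, B batch, C clone, P patient.

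**1. One clone per patient, patients tested against networks.** Degrees of freedom are 10 − 1 = 9 and 10 × (15 − 1) = 140; the critical value is 1.947. With clone share r of total variance and no batch variance, the ratio of expected mean squares is 1 + 15r/(1 − r). At r = 0.10 this is 1 + 1.5/0.9 = 2.67, and the false-positive rate is P(F(9,140) > 1.947/2.67) = 0.68.

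**2. Clones or batches differ within a patient, patients still tested against networks.** Let r be the share of variance that is constant within a batch of five (clone, batch or both). Simulation, 20,000 runs per value.

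| Share r | One clone per patient | One clone per batch |
|---|---|---|
| 0.05 | 38% | 12% |
| 0.10 | 68% | 21% |
| 0.20 | 93% | 43% |
| 0.30 | 98% | 61% |
| 0.50 | >99% | 82% |

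**3. One clone per patient, patients tested against batch within patient.** Degrees of freedom are 9 and 10 × (3 − 1) = 20; the critical value is 2.393. The ratio of expected mean squares is (N + 5B + 15C)/(N + 5B). With N = 1, B = 0.25 and C = 0.1 it is 3.75/2.25 = 1.67, and P(F(9,20) > 2.393/1.67) = 0.24.

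| Batch variance | C = 0.1 | C = 0.25 | C = 0.5 |
|---|---|---|---|
| 0.25 | 24% | 55% | 82% |
| 0.5 | 16% | 37% | 65% |

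So the nested test alone does not repair the one-clone case.

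**4. A different clone in each batch, patients tested against batch/clone within patient.** The expected mean squares are N + 5(B + C) + 15P for patients and N + 5(B + C) for batch/clone. They are equal when P = 0, so the test holds its level; simulation gave 4.7% to 5.2% for r from 0.05 to 0.50.

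**5. Power of the layout in step 4.** With a clone share of 0.1 to 0.2, power is 0.72 to 0.60 if patients account for 0.2 of total variance, and 0.88 to 0.78 if they account for 0.3.

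**The case against.** A reader might infer that the protocol uses one clone per patient and that the inter-patient objective therefore cannot be met. The text does not say so. Section 8.3 speaks of lines and clones in the plural, is openly a summary, and points to published methods. The independence of the batches in 10.1 is undefined, and batches from different clones fit the wording equally well. This part of the objection stands: the confounding is conditional. Even with one clone each, the between-patient component estimates patient plus clone variance, which bounds patient variance from above. That is useful in a study meant as a first estimate of feasibility.

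A reader might also infer that clone noise would produce spurious clinical predictors in section 10.3. It would not. Clone effects drawn independently of age, sex or stroke severity act as outcome error: they lower power but do not themselves create associations. Section 10.3 already says the sample is too small to identify independent predictors.

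The unnamed second factor of the ANOVA could be batch, and the sentence on inter- and intra-patient variance is an expectation, not a formal decision rule. But 10.2 names no batch or clone level. Under one clone per patient, testing patients against a patient-by-batch interaction (df 9 and 18, no batch variance) still gives 27%, 53% and 84% false findings at clone shares of 0.05, 0.10 and 0.20.

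Finally, requiring two or three validated clones from everyone would not be a mere wording change. Section 4.4 rests on what 15 subjects allow within two years: one line each is 15 lines, three each would be 45. Controls come from a repository, and whether it holds further clones is unknown. This stands, and the fix below does not require new clones.

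**Conclusion.** The point holds in conditional form. The protocol leaves open the number of clones per subject and their relation to batches, while 10.2 compares only patients with networks. With one clone per patient, patient and clone variance are inseparable. With clones or batches differing within a patient, treating networks as independent still overstates the evidence for patient differences. Both readings therefore need a change to 10.2.

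The size is illustrative. The rates rest on zero patient variance, equal batches, a 5% test and assumed variance shares, and they describe a mechanism, not a measured property of these cultures. The primary outcome, a descriptive fraction of functional networks, does not depend on this comparison. The change is a cheap improvement that alters what may be concluded on the secondary objective.

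**What to change.** - **Section 10.2:** nest networks within batch, and within clone where more than one is used, within patient. Test between-patient variance against batch/clone within patient, not against networks.
- **Section 10.1:** record the clone used for each batch. Where more than one validated clone of a subject is already available, spread the batches over different clones. Clone and batch then stay confounded with each other, but both lie below patient.
- **Reporting:** where a subject has only one clone, call the component between-line variance (patient plus clone), treat it as an upper bound on patient variance, and draw no claim of patient-specific vulnerability from it.

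**Cost.** Protocol wording and a clone log; the numbers of networks and batches do not change. The test has 20 error degrees of freedom instead of 140 for ten patients, with the power shown in step 5 of the working where each batch has its own clone. The conclusion is more cautious where only one clone exists.
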